4.3. Region of Pooled Countries

The countries will be pooled to 2 regions as [Table 2](#) for the analysis.

Table 2: The Region of Pooled Countries

Region	Country
United States	United States
Other	Japan, Czech Republic, Poland, Russia, Canada, Spain, Israel, Finland

4.4. Multiple Comparisons and Multiplicity

A fixed-sequence (hierarchical) testing procedure will be implemented to control the type 1 error rate at 0.05. The sequence of comparisons will be as follows:

1. mean change from baseline (28-day run-in period) in the monthly average number of headache days of at least moderate severity during the 12-week period after the 1st dose of study drug for the TEV 48125 675/225/225 mg treatment group versus the placebo treatment group
2. mean change from baseline (28-day run-in period) in the monthly average number of migraine days during the 12-week period after the 1st dose of study drug for the TEV 48125 675/225/225 mg treatment group versus the placebo treatment group
3. mean change from baseline (28-day run-in period) in the number of headache days of at least moderate severity during the 4-week period after the 1st dose of study drug for the TEV 48125 675/225/225 mg and TEV 48125 675 mg/placebo/placebo treatment group versus the placebo treatment group
4. proportion of patients reaching at least 50% reduction in the monthly average number of headache days of at least moderate severity during the 12-week period after the 1st dose of study drug for the TEV 48125 675/225/225 mg treatment group versus the placebo treatment group
5. mean change from baseline (28-day run-in period) in the monthly average number of headache days of at least moderate severity during the 12-week period after the 1st dose of study drug for the TEV 48125 675 mg/placebo/placebo treatment group versus the placebo treatment group
6. mean change from baseline (28-day run-in period) in the monthly average number of days of use of any acute headache medications during the 12-week period after the 1st dose of study drug for the TEV 48125 675/225/225 mg treatment group versus the placebo treatment group

7. proportion of patients reaching at least 50% reduction in the monthly average number of headache days of at least moderate severity during the 12-week period after the 1st dose of study drug for the TEV 48125 675 mg/placebo/placebo treatment group versus the placebo treatment group
8. mean change from baseline (28-day run-in period) in the monthly average number of days of use of any acute headache medications during the 12-week period after the 1st dose of study drug for the TEV 48125 675 mg/placebo/placebo treatment group versus the placebo treatment group
9. mean change from baseline (28-day run-in period) in the monthly average number of migraine days during the 12-week period after the 1st dose of study drug for the TEV 48125 675 mg/placebo/placebo treatment group versus the placebo treatment group
10. mean change from baseline (28-day run-in period) in the monthly average number of headache days of at least moderate severity during the 12-week period after the 1st dose of study drug for the TEV 48125 675/225/225 mg treatment group versus the placebo treatment group in patients not receiving concomitant migraine preventive medications
11. mean change from baseline (28-day run-in period) in the monthly average number of headache days of at least moderate severity during the 12-week period after the 1st dose of study drug for the TEV 48125 675 mg/placebo/placebo treatment group versus the placebo treatment group in patients not receiving concomitant migraine preventive medications
12. mean change from baseline (day 0) in disability score, as measured by the HIT-6 at 4 weeks after administration of the last (3rd) dose of study drug for the TEV 48125 675/225/225 mg treatment group versus the placebo treatment group
13. mean change from baseline (day 0) in disability score, as measured by the HIT-6 at 4 weeks after administration of the last (3rd) dose of study drug for the TEV 48125 675 mg/placebo/placebo treatment group versus the placebo treatment group

If the resulting 2-sided p-value from the first comparison is ≤ 0.05 , then the next comparison of interest will be interpreted inferentially at the alpha level of 0.05. This process will continue either until all comparisons of interest are interpreted inferentially or until the point at which the resulting 2-sided p value for a comparison of interest is >0.05 . At the point where $p > 0.05$, no further comparisons will be interpreted inferentially.

4.5. Handling Withdrawals and Missing Data

If a patient has ≥ 10 days of e-diary data after 1st dose of the study drug, his/her monthly average number of days/hours of efficacy variables *during the 12-week period* or monthly number of days/hours of efficacy variables *during the 4-week period* will be prorated to 28 days.

Multiple imputation (MI) method will be applied on the primary variable as sensitivity analyses. The methods will be described in detail in Section 6.2.3.

A patient's monthly number of days/hours of efficacy variables *during the 4-week period* after each dose of study drug will be calculated for months 1, 2, and 3. If a patient has missing diary

days when calculating the monthly variables, the following method will be used to handle the missing data.

- If a patient has ≥ 10 days of e-diary data for a month, the monthly number of days/hours of efficacy variables will be prorated to 28 days for that month.
- If a patient has < 10 days of e-diary data for a month, the monthly number of days/hours of efficacy variables will be considered as missing.

The weekly number of headache days of at least moderate severity and migraine days will be calculated for the patients' first 28 calendar days of diary data after the 1st dose of study drug. Each week is defined as 7 calendar days counted from the 1st dose date. If a patient has missing diary days when calculating the weekly variables, the following method will be used to handle the missing data.

- If the patient has ≥ 3 days of e-diary data for a week, the weekly number of days of efficacy variables will be prorated to 7 days for that week.
- If the patient has < 3 days of e-diary data for a week, the weekly number of days of efficacy variables will be considered as missing for that week.

The missing questionnaire items handling for the MSQOL questionnaire ([Appendix D](#)) is discussed in [Appendix E](#): scoring instruction for MSQOL.

4.6. Study Days and Visit Windows

Study days will be numbered relative to the 1st day of study drug administration. The start of treatment (visit 2 or day 1) is defined as the date on which a patient takes the 1st dose of study drug, as recorded on the study drug administration CRF. Days will be numbered relative to study drug start (i.e., ..., -2, -1, 1, 2, ...; with day 1 being the start of study drug and day -1 being the day before the start of study drug).

The 4-week (28-day) visit windows for the e-diary based efficacy endpoints will be determined based on the actual dosing day. The run-in phase is defined as day -28 to -1 before the 1st injection on day 1. Treatment phase including month 1, 2 and 3 is from the beginning of the 1st injection of study drug to visit 5/day 84 or the end of treatment visit. The 3-month visit windows are separated by each dosing date/time. Month 1 is from the date/time of the 1st dose of study drug administration on day 1 to the date/time just before the 2nd dose. Month 2 is from the date/time of the 2nd dose to the date/time just before the 3rd dose. Month 3 is from the date/time of the 3rd dose to the end of the study on day 84 approximately.

Throughout this document, all by month efficacy summaries for the headache data will refer to these visit windows.

The weekly (7-day) windows for calculating the weekly efficacy endpoints for the first 28 days will be determined based on the 1st dosing day. The first week is from day 1 to day 7, the second week is from day 8 to day 14, the third week is from day 15 to day 21, and the fourth week is from day 22 to day 28. Only the days between the first and the second dose will be included.

For all other by-visit summaries, if there are multiple assessments at a postbaseline visit then the last non-missing assessment at that visit will be used for the summary. This includes assessments at the scheduled and unscheduled visits.

Endpoint for analyses and summaries is the last observed postbaseline data. For patients who withdraw from the study, their safety data at the early termination visit will be excluded from the by-visit summaries but will be included in the endpoint summaries.

5. STUDY POPULATION SUMMARY

5.1. General

The ITT population will be used for all study population summaries unless otherwise noted. Summaries will be presented by treatment group, all TEV-48125 and overall unless otherwise noted.

For continuous variables, descriptive statistics (n, mean, SD, SE, median, minimum, and maximum) will be provided. For categorical variables, patient counts and percentages will be provided. Categories for missing data will be presented if necessary.

5.2. Patient Disposition

Patients screened, screening failures, and the reasons the patients were not randomized will be summarized only for the overall group using patient counts.

Patients randomized, patients randomized but not treated, patients in the safety population, ITT population, FAS and per-protocol analysis set, patients who complete the study, and patients who withdraw from the study will be summarized using descriptive statistics. Patients who withdraw from the study will also be summarized using descriptive statistics by reason for withdrawal. The denominator for calculating the percentages will be the number of ITT population.

5.3. Demographics and Baseline Characteristics

The demographic data including date of birth (or year of birth), sex, country, ethnicity and race will be collected at the screening after the patient signs informed consent. Patient's demographics and baseline characteristics (weight, height, and body mass index, years of migraine, concomitant preventive medication use for migraine, use of topiramite or onabotulinumtoxinA for migraine in the past, and any triptans/ergots during baseline) will be summarized for the ITT population.

The baseline e-diary efficacy variables listed in Section 4.2, baseline HIT-6 scores, and baseline MSQOL scores will be summarized by treatment group for the ITT population.

For continuous variables, treatment groups will be compared using an analysis of variance with treatment as a factor. For categorical variables, treatment groups will be compared using a Pearson's chi-square test (or Fisher's exact test if cells sizes are too small).

5.4. Medical History

All medical history abnormalities will be coded using the Medical Dictionary for Regulatory Activities (MedDRA). The incidence of medical history abnormalities will be summarized by system organ class (SOC) and preferred term (PT). Patients are counted only once in each SOC and only once in each PT.

5.5. Prior Medications or Therapy

All prior medications or therapy will be coded using the World Health Organization dictionary of medical codes (WHO Drug). The incidence of prior medications or therapy will be summarized using descriptive statistics by therapeutic class and PT. Patients are counted only once in each therapeutic class category, and only once in each PT category. Prior medications will include all medications taken prior to the 1st study drug treatment.

The subset of prior medications will be summarized for the following categories.

- preventive migraine medication
- triptans and ergots
- non-steroidal anti-inflammatory drugs (NSAIDs) for migraine/headache
- NSAIDs for reasons other than migraine/headache
- opioids for migraine/headache
- opioids for reasons other than migraine/headache
- other

5.6. Electrocardiography

Electrocardiogram findings (normal, abnormal, and missing) at baseline will be summarized using descriptive statistics.

5.7. Physical Examinations

Physical examinations results will be listed. Patients with at least 1 abnormal finding (overall) and abnormal findings for each category will be summarized.

5.8. Protocol Violations

Patients with at least 1 protocol violation for each category will be summarized using descriptive statistics.

5.9. Childbearing Potential

All patients must be of nonchildbearing potential as defined in protocol Section 4.1. Information related to childbearing potential will be collected and listed.

6. EFFICACY ANALYSIS

6.1. General

The efficacy data for this study consist of headache related questions responses (e.g., occurrence of headache, duration of headache in each day, maximum severity of headache, and acute migraine - specific medication use) collected daily using an electronic headache diary device.

In addition, the following questionnaires will be used for the assessments of migraine impairment, quality of life and satisfaction of treatment etc. during the study (see [Table 1](#) for the schedule of the assessments).

- migraine-related disability using the HIT-6 (see [Appendix C](#))
- migraine-specific quality of life, as measured by the MSQOL questionnaire (see [Appendix D](#))
- health status, as measured by the EQ-5D-5L questionnaire (see [Appendix F](#))
- patient depression status, as measured by the PHQ-2 and the PHQ-9 (see [Appendix G](#))
- patient work productivity and activity impairment, as measured by the WPAI questionnaire (see [Appendix H](#))
- assessment of patient satisfaction, as measured by the PGIC scale (see [Appendix I](#))

The **monthly average number of days or hours** of efficacy variables (e.g., days of headache with at least moderate severity, migraine days, days of headache with any severity, total hours of headache with any severity, total hours of headache with at least moderate severity, days of use of any acute headache medications, days with nausea or vomiting, days with photophobia and phonophobia etc.) **during the 12-week period** after the 1st dose of study drug will be derived and normalized to **28** days equivalent using the following formula.

$$\frac{\sum \text{Days or hours of efficacy variable over the 12 week period}}{\sum \text{Days with assessments recorded in the eDiary for the 12 week period}} \times 28 \quad (1)$$

The **monthly number of days or hours** of efficacy variables **during a 4-week period** after each dose will be derived and normalized to **28** days equivalent using the following formula, where monthly data separated by each visit of study drug dosing will be used.

$$\frac{\sum \text{Days or hours of efficacy variable during the 4 week period}}{\sum \text{Days with assessments recorded in the eDiary for the 4 week period}} \times 28 \quad (2)$$

The **baseline values** will be calculated using all data collected in the run-in period.

$$\frac{\sum \text{Days or hours of efficacy variable during the run – in period}}{\sum \text{Days with assessments recorded in the eDiary for the run – in period}} \times 28 \quad (3)$$

The *percentage of reduction* in the monthly average number of an efficacy variable will be calculated as

$$\frac{\text{baseline value} - \text{postbaseline value}}{\text{baseline value}} \times 100\% \quad (4)$$

where the baseline value is calculated by formula (3) and the postbaseline value in the equation is calculated by formula (1) for the variables *during the 12-week period* or by formula (2) for the variables *during the 4-week period* after each dose for months 1, 2 and 3.

The *baseline values* for calculating the change from baseline of the weekly number of days of the efficacy variables will use all data collected in the run-in period and be calculated as

$$\frac{\sum \text{Days of efficacy variable during the run-in period}}{\sum \text{Days with assessments recorded in the eDiary for the run-in period}} \times 7 \quad (5)$$

The *weekly number of days* of efficacy variables (e.g., days of headache with at least moderate severity, migraine days) for each week during the 4-week period after the 1st dose of study drug will be derived and normalized to 7 days equivalent using the following formula.

$$\frac{\sum \text{Days or hours of efficacy variable during the 7 days period}}{\sum \text{Days with assessments recorded in the eDiary for the 7 days period}} \times 7 \quad (6)$$

The FAS will be used for all efficacy analyses. Summaries will be presented by treatment group as randomized, unless otherwise noted. Descriptive statistics for all efficacy data will be presented by month (or week) and over 12-week period.

The primary and secondary endpoints analysis listed in Section 4.4 will be repeated for the per-protocol analysis set.

6.2. Primary Efficacy Variable(s) and Analysis

For the purpose of this study, a headache day of at least moderate severity will be defined as a calendar day (00:00 to 23:59) where the patient reports:

- a day with headache pain that lasts ≥ 4 hours with a peak severity of at least moderate severity
- or
- a day when the patient used acute migraine-specific medication (triptans or ergots) to treat a headache of any severity or duration

The derivation logic is presented in [Appendix B](#).

6.2.1. Variable Definition

The primary efficacy variable is the change from baseline in the monthly average number of headache days of at least moderate severity *during the 12-week period* after the 1st dose of study drug. The baseline values of the monthly number of headache days of at least moderate severity will be derived using formula (3) in Section 6.1. The postbaseline values will be derived using formula (1), and *the change is* calculated as *postbaseline value – baseline value*.

6.2.2. Primary Analysis

The hypothesis testing for the primary analysis is:

$$H_o : \delta_1 = \delta_2 \quad vs \quad H_a : \delta_1 \neq \delta_2$$

where δ_1 and δ_2 are the estimates of mean change from baseline in the monthly average number of headache days of at least moderate severity for the TEV-48125 treatment group and the placebo group respectively. The estimated difference of TEV-48125 675/225/225 mg versus the placebo and TEV-48125 675/placebo/placebo mg versus the placebo will be tested following the pre-specified fixed sequence as described in Section 4.4.

An analysis of covariance (ANCOVA) method will be applied for the primary analysis. The model will include treatment, sex, region (Table 2), and baseline preventive migraine medication use (yes/no) as fixed effects; the baseline number of headache days of at least moderate severity and years since onset of migraines as covariates. The least square (LS) means for the treatment groups, LS means and corresponding 95% confidence intervals for the treatment differences (TEV-48125 – placebo), and associated p-values will be provided.

The following sample SAS code pertains to the primary analysis.

```
ODS OUTPUT DIFFS=XXX LSMEANS=XXX TESTS3=XXX;
PROC MIXED DATA=XXX;
    CLASS TREAT SEX BMU REGION;
    MODEL CHG=BASE YOD BMU SEX TREAT REGION/S;
    LSMEANS TREAT/PDIFF CL ALPHA=0.05;
RUN;
```

The normality of the residuals from the ANCOVA model will be checked using Shapiro Wilk's normality test. In case that the Shapiro Wilk's test has a p value ≤ 0.01 , Wilcoxon rank-sum test will be conducted as the primary analysis using SAS procedure NPAR1WAY for each active treatment group and placebo group. P value based on normal approximation from this procedure will be selected for the treatment comparison. The ANCOVA analysis will be performed as a supportive analysis.

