- sc administration of 675 mg of TEV-48125 at visit 2 followed by monthly sc placebo
- monthly sc administration of placebo

(Note: For this study, monthly dosing refers to dosing approximately every 4 weeks [28 days].)

Randomization will be performed using electronic interactive response technology (IRT). Patients will be stratified based on sex, country, and baseline preventive migraine medication use (yes, no) to ensure balance for the covariates (treatment group, preventive migraine medication use, country, and sex). The total number of patients receiving concomitant preventive medication during the study will not exceed 30% of the total sample size of the study.

Blinded treatment will be administered sc once monthly (i.e., approximately every 4 weeks) for a total of 3 doses. First treatment administration will occur at visit 2 (day 0), and additional doses will be administered at visits 3 and 4. Final study assessments will be performed at visit 5 (EOT visit), approximately 4 weeks after administration of the 3rd and final dose of study drug.

Headache information will be captured daily during the entire study using an electronic headache diary device. Assessments of migraine-related disability and change in quality of life (using the HIT-6, 2-item Patient Health Questionnaire [PHQ 2]/9-item Patient Health Questionnaire [PHQ - 9], Migraine-Specific Quality of Life [MSQOL] questionnaire, 5 response level EuroQol-5 Dimension [EQ-5D-5L] questionnaire, Patient Global Impression of Change [PGIC] scale, and Work Productivity and Activity Impairment [WPAI] questionnaire); safety evaluations; blood draws for pharmacokinetic, immunogenicity, and biomarker analysis; and urine sampling for biomarker analysis will be performed throughout the study according to the schedule of assessments ([Table 1](#)). In addition, patients who consent to pharmacogenomic assessment will provide a blood sample for testing.

[figure not shown]

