2.4.2. Blinding/Unblinding

This is a randomized study with stratification based on sex, country, and baseline preventive migraine medication use (yes, no). Each patient will undergo randomization in a 1:1:1 ratio within the stratum to which he or she belongs to receive 1 of the 2 TEV 48125 dose regimens or placebo, as assigned by the IRT. The IRT will manage initial drug supply, maintenance of adequate study drug supplies on site, and study randomization centrally. At the time of each study visit, the IRT will be queried, and site personnel will retrieve and administer a 1.5 mL volume from each syringe contained in the appropriately numbered kit(s).

The sponsor, investigators, study staff (except for staff involved in bioanalytical analyses), and patients will be blinded to treatment assignment. A computer-generated master randomization list will be provided to drug packaging facilities. Packaging vendor(s) will package active drug and placebo into single-visit kits according to Good Manufacturing Practice procedures. Kits will be identical in appearance and contain 1 prefilled syringe with active drug or placebo. Adequate

kit supply for upcoming study visits will be managed by IRT and kept (refrigerated at 2°C to 8°C) on site.

In case of a serious adverse event or pregnancy, or in cases when knowledge of the study drug assignment is needed to make treatment decisions, the investigator may unblind the patient's drug assignment as deemed necessary, mainly in emergency situations. Individual treatment codes, indicating the treatment randomization for each randomized patient, will be available to the investigator(s) and/or pharmacist(s) at the study center via the IRT, both via telephone and internet. If possible, the sponsor should be notified of the event prior to breaking of the code. If this is not possible, the sponsor should be notified immediately afterwards, and the patient's drug code assignment should not be revealed. Breaking of the treatment code can always be performed by the site without prior approval by the sponsor.

When a blind is broken, the patient will be withdrawn from the study, and the event will be recorded onto the CRF. The circumstances leading to the breaking of the code should be fully documented in the investigator's study files and in the patient's source documentation. Treatment assignment should not be recorded in any study documents or source document.

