6.2.3. Sensitivity Analysis

6.2.3.1. MMRM Analysis

A mixed-effects repeated measures (MMRM) analysis model will be implemented to estimate the mean change from baseline in the monthly average number of headache days of at least moderate severity for the overall 3 months treatment period and by each month to support the primary analysis.

Each patient's monthly number of headache days of at least moderate severity *during the 4-week period* will be calculated by formula (2) in Section 6.1 based on the e-diary responses for that

month. If a patient is early terminated or has intermittent missing days and has less than 10 days of e-diary entries for a month, that month value will be considered as missing as described in Section 4.5.

The MMRM model will include baseline value, treatment, sex, region, baseline preventive migraine medication use (yes/no), years since onset of migraines, month and treatment-by-month interaction as fixed effects, and patient in the repeated statement as a random effect. The unconstructed covariance structure will be used for the repeated observations within a patient. LS means for the treatment groups, LS means for the treatment differences (TEV-48125 - placebo), and corresponding 95% confidence intervals and associated p-values will be calculated by month and for the overall treatment period.

The following SAS code pertains to the MMRM analysis.

```
ODS OUTPUT DIFFS=XXX LSMEANS=XXX TESTS3=XXX;
PROC MIXED DATA=XXX METHOD=REML;
    CLASS USUBJID MONTH TREAT SEX BMU REGION;
    MODEL CHG=BASE YOD BMU SEX TREAT MONTH TREAT*MONTH/S;
    REPEATED MONTH / SUBJECT=USUBJID TYPE=UN R;
    LSMEANS TREAT TREAT*MONTH/PDIFF CL ALPHA=0.05;
RUN;
```

The LS means±SE of monthly change from baseline values estimated by MMRM will be plotted by month for each treatment group.

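### Randomisation is stratified by country, but the ANCOVA adjusts only for US versus Other: mildly conservative if the pooled countries differ, and cheap to align

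*SAP*

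**What the plan says.** Section 2.1 sets the strata: "Patients will be stratified based on sex, country, and baseline preventive migraine medication use (yes, no". Sections 2.4.2 and 7.2 repeat this, and Section 2.1 also names country among the covariates to be balanced.

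Section 4.3 then coarsens country for analysis: "The countries will be pooled to 2 regions". One is the United States. The other is "Japan, Czech Republic, Poland, Russia, Canada, Spain, Israel, Finland". No reason is given, and there is no expected enrolment by country.

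The primary ANCOVA in Section 6.2.2 keeps sex and preventive use but takes region in place of country: "The model will include treatment, sex, region (Table 2), and baseline preventive migraine medication use (yes/no) as fixed effects". Its code agrees: "MODEL CHG=BASE YOD BMU SEX TREAT REGION/S". Section 6.3.2 uses the same terms for the secondary diary endpoints and HIT-6, and the multiple-imputation analysis in Section 6.2.3.2 reuses the primary model.

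The MMRM in Section 6.2.3.1 is internally inconsistent. The text says "The MMRM model will include baseline value, treatment, sex, region, baseline preventive migraine medication use (yes/no), years since onset of migraines", but the code is "MODEL CHG=BASE YOD BMU SEX TREAT MONTH TREAT*MONTH/S". REGION appears in the CLASS line and nowhere in MODEL.

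**The concern.** Stratifying by country balances the arms within each country, so differences between countries largely drop out of the treatment contrast. A model that includes country takes the same differences out of the residual. A model with only US versus Other leaves the differences among the eight pooled countries in the residual. The estimate is as precise as the design made it, but its reported standard error is larger than its true sampling error.

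The default test in eleven of the thirteen steps in Section 4.4 is an ANCOVA. Planned power is close to 90% with no reserve, and one p-value above 0.05 ends inference for all later steps. Some precision bought at randomisation may therefore go unused.

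**Working it through.** **The plan's own figure.** Section 2.3 gives a difference of 1.7 days, SD 6.29, two-sided 0.05 and 289 evaluable patients per arm. SE = 6.29 × √(2/289) = 0.5233. Power = Φ(1.7/0.5233 − 1.96) = Φ(1.289) = 0.901. With 15% discontinuation, 289/0.85 = 340. The stated sample size is reproduced.

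**Cost in degrees of freedom.** Country has nine levels and region two, so country adds 7 parameters. At N = 867 the residual df fall from 859 to 852 and the critical t moves from 1.96273 to 1.96275. If country explains nothing, power stays at 0.9006.

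**Effect on the standard error.** The SAP gives neither enrolment by country nor a country effect, so both are assumed. Half the patients are in the US. The others hold 12, 10, 10, 8, 4, 3, 2 and 1% of the total, that is 0.24, 0.20, 0.20, 0.16, 0.08, 0.06, 0.04 and 0.02 of Other. The within-country residual SD is 6.29 (variance 39.56). Let τ be the SD between countries within Other.

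- The squared shares sum to 0.1752, so the variance left in the residual by the region model is 0.5 × (1 − 0.1752) × τ² = 0.4124 τ².
- SE ratio, region over country: R = √(1 + 0.4124 τ²/39.56).
- The true sampling SD stays at about 0.5233, because the design balances country. So for the region model, type I error ≈ 2[1 − Φ(1.96 R)], and power ≈ Φ((1.7 − 1.96 × 0.5233 R)/0.5233).

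| τ (days) | R | Region-model SE | Type I error | Power |
|---|---|---|---|---|
| 0 | 1.000 | 0.523 | 0.050 | 0.901 |
| 1 | 1.005 | 0.526 | 0.049 | 0.900 |
| 2 | 1.021 | 0.534 | 0.046 | 0.894 |
| 3 | 1.046 | 0.547 | 0.040 | 0.885 |

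**Check by simulation.** Permuted blocks within country × sex × preventive use, N = 867, the same shares, 1,500 trials per setting. Under no treatment effect:

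| τ (days) | Mean SE, region | Mean SE, country | Type I, region | Type I, country |
|---|---|---|---|---|
| 0 | 0.5225 | 0.5229 | 0.055 | 0.055 |
| 1 | 0.525 | 0.523 | 0.048 | 0.049 |
| 2 | 0.534 | 0.524 | 0.041 | 0.045 |
| 3 | 0.547 | 0.524 | 0.036 | 0.050 |

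Monte Carlo error of the rejection rates is about 0.006. The SE ratios for τ = 1, 2 and 3 are 1.004, 1.020 and 1.045, in line with the formula.

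**Effect on arm means.** The code requests `LSMEANS TREAT` without observed-margin weights, so class levels are weighted equally. For a balanced additive model with 1,020 patients and half in the US, the SE of an arm mean with region is 6.29/√340 = 0.341. With country, and the other eight countries equal at 63.75 patients each, it is 6.29 × √(1/340 + (1/81)/510 + 8 × (1/81)/63.75 − 1/1020) = 0.374. It grows further when the small countries are unequal in size. Treatment differences are not affected.

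**The case against.** The strongest reply is that a prespecified, coarser factor is a legitimate choice. It never inflates type I error, and the gain rests on a quantity the SAP does not give. The model already adjusts for baseline headache days and years since onset, so only country differences in adjusted change count. A between-country SD of 3 days would be 9/(9 + 39.56) = 19% of the variance within Other, which is an extreme case. At 1 day the loss is about a fifth of a power point. All of this stands and limits the point to efficiency.

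Four stronger readings are tempting and are not supported:

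- A reader might infer that the primary test is invalid. It errs on the conservative side.
- A reader might infer that the pooled countries are known to differ. No figure in the SAP shows this.
- A reader might infer that every ANCOVA and MMRM adjusts for US versus Other. The MMRM as coded adjusts for no geography.
- A reader might infer that using country is free. It costs 7 degrees of freedom, needs a pooling rule and, with equal-weight LS means, enlarges the arm-mean standard errors. Observed-margin weights remove that last cost.

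The reach is also limited. Steps 4 and 7 of the sequence are CMH tests stratified by preventive use only. If the Shapiro-Wilk p-value is 0.01 or below, an unstratified Wilcoxon test becomes the primary analysis, and only the supportive ANCOVA would gain from the change.

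**Conclusion.** The mismatch between design and model is real and stands in the text and code of Section 6.2.2. Its consequence is a standard error for the treatment difference that is too large by about 0.5%, 2% and 4.5% at an assumed between-country SD of 1, 2 and 3 days within Other. The corresponding power loss is about 0.2, 0.7 and 1.7 points. There is no loss if these countries do not differ. The sizes assume half the patients in the US, the country shares listed, and a within-country SD of 6.29. This is a cheap improvement and not a threat to validity. The disagreement between MMRM text and code is a plain inconsistency that needs correcting whichever geography term is chosen.

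**What to change.** - **Sections 6.2.2 and 6.3.2:** replace region by country in the ANCOVA text and in the CLASS and MODEL lines.
- **Section 4.3:** fix, before unblinding, a rule for pooling very small countries: a minimum size and a named country to join. Say how it applies in subsets such as the patients without preventive medication in steps 10 and 11. US/Other can stay for descriptive display.
- **LS means:** add the OM option to the ANCOVA's `LSMEANS TREAT` statement so that arm means are not averaged equally over countries. This also reweights sex and preventive use to the study population, so arm means will differ from those now planned. Treatment differences in this additive model do not change.
- **Section 6.2.3.1:** put the same geography term in the MMRM text and its MODEL statement. If OM is used there, state the weights for month, since it would reweight months as well.

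If the sponsor prefers the two-level region, the SAP should give the reason, and the MMRM code should still be corrected.

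Cost: 7 degrees of freedom out of about 859, one pooling rule, and a few lines of wording and code.
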